4.1 Rationale for study design

The clinical development program of siponimod has demonstrated both a favorable efficacy and benefit: risk profile in RMS and SPMS patients. While there is a fair amount of data on the overall safety profile of siponimod, less data exists to describe the safety and tolerability profile

during conversion from existing DMTs to siponimod in a broader population than included in the Phase II and Phase III development program and to determine how health outcomes changes when patients start treatment with siponimod both short- and long-term.

This prospective open-label treatment study design supports the need for increased human exposure to a new medicine to further evaluate the safety on the immediate conversion of oral injectable, and infusion DMTs to siponimod in patients with advancing RMS. A treatment period of 6 months will allow achieving assessment of potential overlapping immune effects from previous DMT at steady state of oral siponimod. Further, this 6-month treatment period will increase the knowledge of the safety profile of siponimod. The data from the study will give HCPs a better understanding of what the potential safety implications will be with an acute conversion of existing DMTs to siponimod.

This study will include a virtual cohort of patients, i.e., the patient will remain in their own home and complete study assessments via an online technology. This virtual cohort of the study is being done in parallel to, but separate from, other sites that will conduct study visits in the traditional manner, i.e., with all assessments performed at the study center. This study design element will potentially offer patients better access to a clinical trial

4.2 Rationale for dose/regimen and duration of treatment

In the siponimod Phase III (EXPAND) trial, siponimod treatment was initiated with a 5-day dose titration, starting with 0.25mg once daily on day 1 and 2, followed by once daily doses of 0.5mg on day 3 (two tablets of 0.25mg), 0.75 mg on day 4 (three tablets of 0.25mg) and 1.25mg on day 5 (five tablets of 0.25mg) to reach the maintenance dose of siponimod 2mg starting on day 6. It is currently unknown whether this titration regimen is needed among patients who are converting from existing S1P receptor modulators (e.g., fingolimod) to siponimod.

Given the recent development of S1P receptor modulators over the last few years in general, transition between emerging S1P treatments has not been broadly assessed. Sustained fingolimod induced receptor internalization of S1P receptors has been demonstrated in a number of separate studies (Jo et al., 2005); (Oo et al., 2007); (Mullershausen et al., 2009). Both siponimod and fingolimod are thought to act as a functional S1P1R antagonist, causing complete internalization and down—regulation of the S1P1 receptor found on lymphocytes (Matloubian et al., 2004); (Chiba et al., 2006); (O'Sullivan et al., 2016). Through this on-going study, there is clinical utility in substantiating the hypothesis that a direct switch between S1P receptor modulators is clinically safe and effective in sustaining therapeutic coverage. Therefore, in this study amendment, we suggest to omit the siponimod titration regimen for only those patients converting from fingolimod strata as part of the investigative approach in understanding the role of titration, or lack of, when converting between the two S1P receptor modulators to ensure patients are not undertreated.

The EXPAND trial demonstrated that 288 (26%) of 1096 patients receiving siponimod and 173 (32%) of 545 patients receiving placebo had 3-month CDP (hazard ratio 0.79, 95% CI 0.65–0.95; relative risk reduction 21%; p=0.013; (Kappos L et al Lancet 2018). Headache, nasopharyngitis, urinary tract infection, and falls were the most frequent adverse events, being reported in more than 10% of patients in both treatment groups. There were no observed cases of Mobitz type II or higher degree atrioventricular block.

Because of the success of siponimod in the EXPAND trial, the data was used as a reference and led to 2mg as the maintenance dose for all the patients in this Phase IIIb study with a 6-month treatment in the core treatment period for all patients. The data collected from this Phase IIIb study will be important to provide a better understanding of the safety profile when acutely converting advancing RMS patients to siponimod from standard of care oral, injectable or infusion DMTs.

4.3 Rationale for choice of control drugs

Not Applicable.

4.4 Purpose and timing of interim analyses/design adaptations

Shortly before the scheduled completion of enrollment in this study, an interim analysis will be performed. Since pre-specification of the parameters relevant for the sample size calculations (disease activity, enrollment rate, and dropout rate) has uncertainty, it is reasonable to re-assess the pre-study assumptions prior to the completion of the enrollment period. For the purpose of earlier dissemination, an interim analysis on the safety data will be conducted at the time of approximately 50 patients completing their Visit 5 (Day 168). This analysis may result in an increase in the total number of patients enrolled in the study. The maximum number of patients is specified in section 5. Additional interim analyses may be conducted at additional time points based on study enrollment to evaluate continued efficacy and safety data (for example, 50% enrollment). These interim analyses will also allow for an evaluation of the infusion strata.

4.5 Risks and benefits

When adhering to the inclusion/exclusion criteria and PIs guidance on safety conditions, providing close clinical monitoring, avoiding prohibited treatments, the risk to patients in this trial will be minimized.

The risk profile of siponimod includes bradyarrhythmia (including conduction effects) occurring post-first dose in patients with heart rate (HR) less than 55 beats per min (bpm) and liver transaminase elevation. Risks associated with S1P modulators, but not observed with siponimod to date include clinically relevant bronchoconstriction, increased frequency of infections, hypertension and posterior reversible encephalopathy syndrome. There may be yet unknown risks to MS patients taking siponimod, which may be serious and unforeseen. There is little data from phase III/IIIb clinical trials asserting safety relevant to acute conversion of siponimod from current standard of care treatments.

With limited treatment options for patients with advancing RRMS and patients progressing to or currently diagnosed with SPMS, siponimod has demonstrated the potential to be an effective treatment that addresses the current unmet needs for this population.

Women of child bearing potential and sexually active males must be informed that taking the study treatment may involve unknown risks to the fetus if pregnancy were to occur during the study. Thus, they must agree to adhere to the contraception requirements outlined in the exclusion criteria in order to participate in the trial. If there is any question that the patient will not reliably comply, they should not be entered or continue in the study.

4.6 Rationale for public health emergency mitigation procedures

During a Public Health emergency as declared by Local or Regional authorities i.e. pandemic, epidemic or natural disaster, mitigation procedures to ensure participant safety and trial integrity are listed in relevant sections. Notification of the Public health emergency should be discussed with Novartis prior to implementation of mitigation procedures, and permitted/approved by Local or Regional Health Authorities and Ethics Committees as appropriate.

5 Population

This study includes advancing RMS patients. Because the transition of disease activity from RRMS to SPMS is not well-characterized, introducing a functional definition of advancing RMS for purposes of this study is aimed to help identify patients who may be demonstrate onset of relatively fixed impairment indicative or worsening disease activity or progressive disease activity.

The study population will consist of out-patient, male and female patients, ≥18-65 (inclusive) years of age, with an EDSS score ≥2.0-6.5, inclusive, with advancing RMS with or without progressive features. The diagnosis of MS with initial relapsing remitting disease course is defined by the 2010 revised McDonald criteria (Polman et al 2011). EDSS >2 defines the beginning of relatively fixed impairment. Worsening denotes an increase in neurological dysfunction and/or disability, with or without evidence of relapses or disease activity on MRI (Lublin et al 2013). Progression denotes the continuous or steady worsening of neurological impairment over at least 6 months (Rovaris et al 2006) not explained by incomplete recovery from relapses (Lublin et al 2013).

Patients who have been previously treated with other MS therapies, such as interferon beta-1a, interferon beta-1b, glatiramer acetate, fingolimod, fumarates (dimethyl fumarate, diroximel fumarate), teriflunomide, natalizumab or ocrelizumab for at least 3 months at the time of consent may participate. Approximately 300-400 patients will be randomized from up to 80 study sites in the USA. The study plans to screen approximately 570 patients.

At the time of enrollment, patients are eligible if they are identified as clinically appropriate advancing RMS patients and eligible to receive siponimod, as well as meeting all other eligibility criteria.

5.1 Inclusion criteria

Patients eligible for inclusion in this study must meet all of the following criteria:

1. Signed informed consent must be obtained prior to participation in the study.

- 2. Male or female aged 18 to 65 years (inclusive) at screening
- 3. Patients with advancing RMS as defined by the principal investigator
- 4. Prior history of relapsing MS (RMS), with or without progressive features, according to the 2010 Revised McDonald or Lublin criteria (Lublin et al 2013)
- 5. Disability status at screening with an EDSS score of >2.0 to 6.5 (inclusive)
- 6. Having been continuously treated with beta-interferons, glatiramer acetate, fingolimod, fumarates (dimethyl fumarate, diroximel fumarate), or teriflunomide for at least 3 months at the time of consent OR having had last natalizumab dose at least 4 weeks before screening OR last ocrelizumab dose 14 weeks prior to screening.

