	 Disability status at screening with an EDSS score of ≥2.0 to 6.5 (inclusive)
	 Having been continuously treated with beta-interferons, glatiramer acetate, fingolimod, fumarates, teriflunomide, natalizumab or ocrelizumab for at least 3 months at the time of consent
	 Patients desiring to start treatment with a DMT investigated in advancing stages of multiple sclerosis.
Key Exclusion criteria	Patients meeting any of the following criteria are not eligible for inclusion in this study. No additional exclusions may be applied by the investigator in order to ensure that the study population will be representative of all eligible patients:
	1. Patients with an active chronic disease (or stable but treated with immune therapy) of the immune system other than MS (e.g., rheumatoid arthritis, scleroderma, Sjogren's syndrome, Crohn's disease, ulcerative colitis, etc.) or with a known immunodeficiency syndrome (AIDS, hereditary immune deficiency, drug-induced immune deficiency).
	 Pregnant or nursing (lactating) women, where pregnancy is defined as the state of a female after conception and until the termination of gestation, confirmed by a positive hCG laboratory test.
	3. Women of child-bearing potential, defined as all women physiologically capable of becoming pregnant, unless

they are using highly effective methods of contraception while taking study treatment and for 30 days (30 = 5 times the terminal half-life of siponimod) after stopping study treatment. Highly effective contraception methods include:

- Total abstinence (when this is in line with the preferred and usual lifestyle of the patient. Periodic abstinence (e.g., calendar, ovulation, symptothermal, post-ovulation methods) and withdrawal are not acceptable methods of contraception
- Female sterilization (have had surgical bilateral oophorectomy with or without hysterectomy), total hysterectomy, or tubal ligation at least six weeks before taking study treatment. In case of oophorectomy alone, only when the reproductive status of the woman has been confirmed by follow up hormone level assessment
- Male sterilization (at least 6 months prior to screening). For female patients on the study, the vasectomized male partner should be the sole partner for that patient

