 - History of or current significant cardiac disease including cardiac failure (NYHA functional class II-IV), myocarditis, cardiomyopathy, angina pectoris or myocardial infarction (within 6 months), unstable angina (within 6 months), stroke (within 6 months), TIA (within 6 months), decompensated heart failure requiring hospitalization (within 6 months) or uncontrolled arterial hypertension
 - Patients receiving treatment with beta-blockers for cardiac disease/comorbidities.
 - Any other condition which, in the opinion of the investigator, has a potential for AV conduction suppression and/or other risk factors that may require expanded cardiac monitoring
 - Patients diagnosed with right bundle branch block, either at the screening visit for entry of the study or during the conduct of the study
- 15. Any of the following pulmonary conditions:
 - History of or active severe respiratory disease, including COPD, or pulmonary fibrosis,
 - Tuberculosis, except for history of successfully treated tuberculosis or a history of prophylactic treatment after positive PPD skin reaction
 - Patient with severe asthma or asthma requiring regular treatment with oral steroids

- 16. Patients with any of the following hepatic conditions prior to screening:
 - history of alcohol abuse, chronic liver or biliary disease
 - total or conjugated bilirubin greater than 1.5 times ULN range, unless in the context of Gilbert's syndrome
 - alkaline phosphatase (AP) greater than 1.5 times the ULN range
 - AST (SCOT), ALT (SGPT) or Gamma-glutamyltransferase (GGT) greater than 3 times the ULN range within the last 6 months
- 17. Any of the following abnormal laboratory values prior to screening:
 - Serum creatinine > 1.7 mg/dL (150 umol/L)
 - White blood cells (WBC) count <3,500/mm3 (<3.5 x 10(9)/L), while on injectable or oral DMT's at screening, except fingolimod
 - Lymphocyte count <500/mm3 (<0.5 x 10(9)/L) while on all DMT's at screening except fingolimod
 - Serum potassium > ULN
 - Or other clinically significant laboratory assessment (i.e. hypomagnesemia or hypokalemia)
 - For patients previously exposed to natalizumab, anti-JCV antibody positive and index > 1.5
- 18. Patients with the following neurological/psychiatric disorders prior to screening:
 - History of substance abuse (drug or alcohol) or any other factor (i.e. serious psychiatric condition) that may interfere with the patient's ability to cooperate and comply with the study protocol

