 - History of or current significant cardiac disease including cardiac failure (NYHA functional class II-IV), myocarditis, cardiomyopathy, angina pectoris or myocardial infarction (within 6 months), unstable angina (within 6 months), stroke (within 6 months), TIA (within 6 months), decompensated heart failure requiring hospitalization (within 6 months) or uncontrolled arterial hypertension
 - History of (within the 6 months) or current cardiac disease such as heart failure NYHA class I, history of myocardial infarction prior to enrollment.
 - Patients receiving treatment with beta-blockers for cardiac disease/comorbidities
 - Any other condition which, in the opinion of the investigator, has a potential for AV conduction suppression and/or other risk factors that may require expanded cardiac monitoring
 - Patients diagnosed with right bundle branch block, either at the Screening visit for entry of the study or during the conduct of the study
- 15. Any of the following pulmonary conditions:
 - History of or active severe respiratory disease, including COPD, or pulmonary fibrosis,
 - Tuberculosis, except for history of successfully treated tuberculosis or a history of prophylactic treatment after positive PPD skin reaction

- Patient with severe asthma or asthma requiring regular treatment with oral steroids
- 16. Patients with any of the following hepatic conditions prior to screening:
 - history of alcohol abuse, chronic liver or biliary disease
 - total or conjugated bilirubin greater than 1.5 times ULN range, unless in the context of Gilbert's syndrome
 - alkaline phosphatase (AP) greater than 1.5 times the ULN range
 - AST (SCOT), ALT (SGPT) or Gamma-glutamyl-transferase (GGT) greater than 3 times the ULN range within the last 6 months
- 17. Any of the following abnormal laboratory values prior to screening:
 - Serum creatinine > 1.7 mg/dL (150 umol/L)
 - White blood cells (WBC) count <3,500/mm3 (<3.5 x 10(9)/L), while on oral DMT's at screening, except fingolimod
 - Lymphocyte count <500/mm3 (<0.5 x 10(9)/L) while on all DMT's at screening except fingolimod
 - Serum potassium > ULN
 - Or other clinically significant laboratory assessment (i.e. hypomagnesemia or hypokalemia)
 - For patients previously exposed to natalizumab, anti-JCV antibody positive and index > 1.5
- 18. Patients with the following neurological/psychiatric disorders prior to screening:

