### **2.3.1 Patient disposition**

Screening phase disposition and study phase disposition will be summarized.

The number and percentage of patients screened, screened passed and screen failed will be summarized for all the screened patients for the screening phase disposition.

For the study phase disposition, the overall number of patients who are screened passed i.e. entered into the study, completed the study and discontinued from the study (and/or treatment) will also be summarized with reasons for premature discontinuation on all enrolled patients.

Patient identification number and whether they completed or discontinued from the study (and/or treatment) will be listed, with date of last dose and primary reason for premature discontinuation.

For each protocol deviation (PD), the number and percentage of patients for whom the PD applies will be tabulated. A separate listing will be provided for the details on the patient identifier having met a specific PD.

The PD's will be distinguished in the below 5 categories as applicable:

- Selection Criteria Not Met - Inclusion/Exclusion criteria

- Patient Not Withdrawn As Per Protocol - Withdrawal criteria met but patient not withdrawn
- Treatment Deviation - Wrong treatment or incorrect dose
- Prohibited concomitant medication
- Other

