**Table 5 Protocol deviations that cause patients to be excluded**

Deviation Code	Text Description	Severity/ Analysis Classify action Code
INCL01	Signed informed consent not obtained prior to participation in the study	49
INCL02	Age of patient is not between 18 to 65 years (inclusive) at screening	49
INCL03	Patient is not with advancing RMS as defined by the principal investigator	49
INCL04	Not having prior history of relapsing MS (RMS), with or without progressive features, according to the 2010 Revised McDonald or Lublin criteria	49
INCL05	Disability status at screening is not defined as EDSS score of $\geq 2.0$ to 6.5 (inclusive)	49
INCL06	Not treated with b-interferons, glatiramer acetate, fingolimod, dimethyl fumarate, or teriflunomide 3 months at IC, had last natalizumab 4 wks prior SCREEN, or had ocrelizumab 14 wks prior SCREEN	49
EXCL01	Patients with an active chronic disease of the immune system other than MS or with a known immunodeficiency syndrome (AIDS, hereditary immune deficiency, drug-induced immune deficiency)	49
EXCL02	Pregnant or nursing (lactating) women, where pregnancy is defined as the state of a female after conception and until the termination of gestation, confirmed by a positive Hcg laboratory test	49
EXCL03a	Women of child bearing potential unless using highly effective methods of contraception while taking study treatment and for 30 days after stopping study treatment	49
EXCL03b	Post-menopausal women and not of child bearing potential if they had 12 months of natural amenorrhea or surgical bilateral oophorectomy, total hysterectomy or tubal ligation at least six week ago	49
EXCL04	Sexually active males unwilling to use a condom during intercourse while taking study treatment and for 30 days (30= 5 times the terminal half-life of Siponimod) after stopping study treatment	49
EXCL05	History of malignancy of any organ system other than localized basal cell carcinoma of the skin treated or untreated within the past 5 years regardless of evidence of local recurrence or metastases	49
EXCL06	Diabetes mellitus, unless well controlled and without known organ complications including but not limited to heart disease reduced renal function, significant retinal pathology or neuropathy	49
EXCL07	Diagnosis of macular edema 1 year prior to screening	49

EXCL08	Patients with active systemic bacterial, viral, or fungal infections or known to have AIDS or have positive HIV antibody	49

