EXCL09	Positive results of screening period testing for serological markers for hepatitis A, B, C and E, indicating acute or chronic infection	49
EXCL10	Negative for varicella-zoster virus IgG antibodies at Screening unless there is other evidence of immunity to VZV based on the CDC criteria	49
EXCL11	Have received any live or live-attenuated vaccines (including for varicella-zoster virus or measles) within 2 months of screening	49
EXCL12	Treated with protocol restricted medication and therapies prior to screening and randomization as defined in exclusion criteria 12	49
EXCL13	Patients with any medically unstable condition as determine by the investigator	49
EXCL14	Any of the conditions or treatments that may affect cardiovascular function as listed in protocol	49
EXCL15	Pulmonary conditions History or active severe respiratory disease or prophylactic treatment or Tuberculosis, except history of successful treatment of TB or severe asthma or asthma with oral steroids	49
EXCL16	Patients with any of the hepatic conditions as described in protocol prior to screening	49
EXCL17	Abnormal laboratory values as defined in exclusion criteria prior to screening	49
EXCL18	Patients with the following neurological, psychiatric disorders prior to screening	49
EXCL19	Use of other investigational drugs at time of enrollment or within prior 30 day or five elimination half-lives or until expected pharmacodynamics effect has returned to baseline whichever is longer	49
EXCL20	History of hypersensitivity to the study drug or to drugs of similar chemical classes	49
EXCL21	Homozygosity for CYP2C9*3/*3 or heterozygous for CYP2C9*2/*3 or CYP*1*3 (to be tested at screening) or refusal to test for CYP2C9 variants	49
EXCL22	Concomitant use of MAYZENT and drugs that cause moderate CYP2C9 and moderate or strong CYP3A4 inhibition	49
EXCL23	Concomitant use of MAYZENT and drugs that cause moderate CYP2C9 and strong CYP3A4 induction	49
EXCL24	Use of cannabinoid or cannabidiol products 30 days prior to screening	49

EXCL25	Any other disease or condition which could interfere with participation in the study according to the study protocol or with ability of patient to cooperate and comply with study procedures	49
TRT01	Siponimod dose adjusted and/or interrupted	49
TRT02	Treatment is interrupted for 4 or more consecutive daily doses, and treatment not re-titrated per protocol	49

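### The WBC exclusion and the infusion-DMT entry rule each read differently in the Protocol summary and in Sections 5.1/5.2, and the SAP does not say which WBC text defines a deviation

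*Protocol*

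**What the plan says.** **WBC exclusion.** Criterion #17 appears twice in the current protocol with the same threshold, below 3,500/mm3, but a different scope.

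- Protocol summary, Key Exclusion criteria #17: "while on injectable or oral DMT's at screening, except fingolimod".
- Section 5.2 #17: "while on oral DMT's at screening, except fingolimod".

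The SAP (Section 4.5, Table 5) records a breach as EXCL17: "Abnormal laboratory values as defined in exclusion criteria prior to screening". SAP 2.3.1 adds that for each deviation "the number and percentage of patients for whom the PD applies will be tabulated".

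**Infusion patients.** Criterion #6 also has two forms.

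- Protocol summary, Key Inclusion criteria #6, ends a list of prior therapies with "natalizumab or ocrelizumab for at least 3 months at the time of consent". Section 5 (Population) says the same: "natalizumab or ocrelizumab for at least 3 months at the time of consent may participate".
- Section 5.1 #6 keeps the 3-month minimum for the injectable and oral drugs, then adds for infusions: "OR having had last natalizumab dose at least 4 weeks before screening OR last ocrelizumab dose 14 weeks prior to screening". SAP Table 5, INCL06, follows this form: "had last natalizumab 4 wks prior SCREEN, or had ocrelizumab 14 wks prior SCREEN".

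**The concern.** Eligibility text should give one answer for one patient. Here two parts of the same protocol version give opposite answers for two kinds of patient.

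For the WBC rule, the difference decides whether some patients on injectables with a low white count start a drug that itself lowers peripheral lymphocytes (Protocol 1.1). Section 5.2 forbids investigators to add exclusions, so a site working from it has no stated WBC threshold to apply to an interferon or glatiramer patient. Section 11.3 requires monitors to verify adherence to the criteria in full. The EXCL17 row of the deviation table will therefore mean different things depending on which page the site and monitor used.

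For the infusion rule, the difference decides whether a patient with less than 3 months of natalizumab or ocrelizumab may enter. These strata were added on purpose, are planned at 80-100 patients (Protocol 12.8.1) and are singled out for interim evaluation (Protocol 12.7), so their entry rule ought to be unambiguous.

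**Working it through.** **The plan's own figure.** Protocol 12.8.1 gives a 95% half-width of 4.9% to 5.6% for N = 300 to 400 at a related-AE rate of 45%. With 1.96 × √(0.45 × 0.55 / N):

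- N = 300: 5.63%
- N = 400: 4.88%

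Both match. Neither conflict enters this formula, so the planned precision is not in question. The rest of the check is a comparison of texts.

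**Conflict (a), applied to one patient.** Take a patient on interferon with WBC 3,000/mm3.

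| Text | Scope of the WBC bullet | Result if lymphocytes < 500/mm3 | Result if lymphocytes ≥ 500/mm3 |
|---|---|---|---|
| Summary #17 | injectable or oral, not fingolimod | excluded | excluded |
| Section 5.2 #17 | oral, not fingolimod | excluded by the lymphocyte bullet | not excluded by any stated WBC or lymphocyte threshold |

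The lymphocyte bullet is the same in both places and covers all DMTs except fingolimod. The disagreement is therefore confined to the last column: injectable patients with WBC below 3,500/mm3 and lymphocytes at or above 500/mm3.

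As to which text was meant, the Amendment 3 rationale for #17 uses the wider wording found in the summary. That suggests the words were lost from 5.2. It is evidence of intent only; the conflict itself is between two current texts.

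EXCL17 refers to the exclusion criteria without restating the bullet, so it cannot resolve the matter.

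**Conflict (b), applied to one patient.** Take a patient treated with an infusion DMT for less than 3 months, whose last dose meets the required gap.

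| Text | 3-month minimum for infusions | Gap since last dose stated | Result |
|---|---|---|---|
| Summary #6 | yes | no | fails |
| Section 5 | yes | no | fails |
| Section 5.1 #6 | no | 4 or 14 weeks | passes |
| SAP INCL06 | no | 4 or 14 weeks | passes |

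The gap itself is not in dispute. Protocol Sections 3 and 8 and SAP 1.1 all state it as a minimum of 4 or 14 weeks. Section 5.1 drops the words *at least* for ocrelizumab, but the Section 8 table supplies them. What remains open is the 3-month minimum alone.

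**Upper limit on numbers.** Infusion patients are planned at 80-100 out of 300-400. The protocol does not pair the ends of the two ranges, so:

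- smallest share: 80/400 = 20%
- largest share: 100/300 = 33%
- non-infusion patients: 300 − 100 = 200 to 400 − 80 = 320

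Conflict (b) can affect some of the first group. Conflict (a) can affect only those of the second group who are on an injectable and fall in the last column of the first table. The documents give neither the injectable share nor the frequency of low WBC, so no count can be derived.

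**Effect on the analysis sets.** Every deviation in SAP Table 5 carries code 49, which Table 7 defines as reported but kept in all analyses. The Safety Set is everyone who took a dose. Neither depends on how the conflicts are resolved.

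**The case against.** The best case on the other side is that little follows from either conflict.

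On (a), the lymphocyte floor protects injectable patients under both texts, blood counts are repeated at each visit, and Appendix 3 interrupts treatment if lymphocytes are confirmed below 0.2 × 10^9/L. An investigator can also use the bullet on other clinically significant laboratory findings. This stands as a limit on the risk: it would be wrong to infer that low-WBC injectable patients enter without any safeguard. It does not remove the conflict, because none of these provisions restores the 3,500/mm3 threshold.

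On (b), the SAP already spells out the 5.1 rule in INCL06, so the deviation table has a definition. That also stands, and it is why only EXCL17 needs a ruling in the SAP. It leaves a site reading the summary or Section 5 with a stricter rule.

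Three stronger readings are tempting, and the documents do not support them.

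- *That the conflict lets ocrelizumab patients start while still B-cell depleted.* Section 1.1 gives a median recovery of 72 weeks (range 27-175), and 14 weeks falls well short of that. But the early start follows from the chosen washout, which applies whichever form of #6 is used.
- *That patients with only remote infusion exposure fill the infusion strata.* This takes 5.1 #6 on its own. The objective concerns patients converting from a current therapy, Section 8 speaks of patients converting from each infusion drug, and Section 8.2 records the last DMT before conversion.
- *That the SAP errs by not summarising time since last infusion.* No objective or endpoint uses that interval, SAP 2.3.2 promises MS history as collected on the eCRF, CD19+ is measured at screening for ocrelizumab patients, and parts of the SAP are redacted. Such a summary would be a useful option, not the repair of an error.

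**Conclusion.** Both conflicts are real and lie in current text.

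The WBC conflict matters more. As written, Section 5.2 admits interferon or glatiramer patients with WBC below 3,500/mm3 and lymphocytes of at least 500/mm3 whom the Protocol summary excludes, and the SAP leaves the matching deviation undefined. The infusion conflict is narrower: it concerns only whether the 3-month treatment minimum applies to natalizumab and ocrelizumab.

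The number of patients affected is unknown. For the infusion rule it cannot exceed the 80-100 planned patients (20-33% of the total).

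A reader might infer that the primary result is compromised. It is not: the Safety Set, the definition of the overall related-AE rate and its planned precision are unchanged. What is at stake is who may enter and what two rows of the deviation table mean. The conclusion assumes that the two versions of each criterion are equally binding, since the protocol does not say which prevails.

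**What to change.** 1. **Section 5.2 #17.** Restore injectables to the WBC bullet so that it matches the Protocol summary. If enrolment has closed, state in the SAP which text EXCL17 is judged against.
2. **Protocol summary #6 and Section 5.** Bring both into line with Section 5.1 #6 and INCL06, so that infusion patients are judged on time since last dose. In 5.1 #6, insert *at least* before the 14-week interval to match the Section 8 table.

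A descriptive summary of weeks from last infusion to first siponimod dose may be added to the SAP if the sponsor finds it useful. It is optional and separate from these corrections.

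**Cost.** A short protocol amendment, with IRB/IEC approval and health-authority approval where required (Section 14.1), passed on to up to 80 sites. There are no new procedures, data or patients. If enrolment has closed, the amendment would no longer change anyone's entry and the SAP statement on EXCL17 is what remains useful. The current SAP version is marked as prior to database lock, so that statement can be added as a SAP amendment if lock has not yet occurred.
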